5.1 Initial sample size justification (500 participants)

From the prevalence of symptoms in IBD patients, it is anticipated that at least 50% of 6,300 predicted respondents to the survey (stage 2) will report one or more symptoms of fatigue, pain, or urgency/faecal incontinence (n=3,150 symptomatic individuals). Of symptomatic participants, it is anticipated that approximately one-third will express an interest in further management for these symptoms and attend one of our clinical sites for routine IBD care (~1,000 individuals available as potential recruits for the present study). Of ~1,000 potential recruits, it is anticipated that 50% (500 individuals) will consent to participate in the OPTIMISE study.

5.1a Revise sample size

Due to the impact of the COVID-19 pandemic on study recruitment, with only 4 of the anticipated 20 NHS sites ever opening, it was necessary (with Steering Group, funder, and ethical approval) to reduce the target sample size from 500 participants to 200 participants and convert this to a feasibility study with the focus on feasibility outcomes (see above). With a sample size of 200 participants, the width of the 95% confidence interval (CI) for the proportion of participants with pathophysiological contributors that are potentially medically treatable will be at most 13.9% (normal approximation CI).

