6.5 General analysis principles

Study participants who express desire for support with IBD-related symptoms and receive the selfreport symptom checklist will be included in descriptive baseline analyses. For study participants who receive algorithm-informed intervention(s), the effect size (e.g., mean change in symptom severity scores) will be estimated. A two-sided p-value and 5% alpha level will be used to declare

statistical significance. However, the focus of this analysis is descriptive. Ninety-five percent confidence intervals (95%Cls) will be reported unless stated otherwise.

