6.8 Analysis of secondary (clinical) outcomes

Prior to algorithm-informed intervention(s):

The proportion of study participants for whom algorithm-informed management is indicated, and the proportion of study participants who decline indicated algorithm-informed management, will be estimated using the same approach taken for the descriptive analysis of the primary outcome(s).

Prior to and following algorithm-informed intervention:

PROMIS scores & Quality of Life scores

Means, standard deviations, and 95%CIs will be calculated for each PROMIS score (i.e., pain T-score, fatigue T-score, and bowel incontinence raw score) and EQ-5D-5L score will be calculated at initial checklist implementation (i.e., baseline) separately by whether intervention is indicated.

Following algorithm-informed intervention:

Change in PROMIS scores & Quality of Life scores

For study participants who receive algorithm-informed interventions for treatable causes of IBDrelated symptoms, PROMIS (for fatigue, pain, and faecal urgency/incontinence symptoms), IBD control score, and EQ-5D-5L scores three months after checklist implementation, after adjusting for relevant confounders, will be estimated. A linear regression model will be constructed for each outcome variable listed in appendix Table 6, adjusting for the baseline measure of that outcome variable, IBD diagnosis (e.g., Crohn's disease or other IBD type), and NHS Trust. Linear regression assumptions – for example, linearity, normally distributed error residuals, and residual homoscedasticity, and multi-collinearity – will be assessed. If data are normally distributed, a normal approximation will be used to estimate 95%CIs. If data are not normally distributed, bootstrap CIs will be estimated (using 1,000 bootstrap samples) because sample sizes may not be sufficiently large to invoke the central limit theorem. If regression models fail to converge, the covariate 'NHS Trust' will be removed.

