6.10 Subgroup analyses

A subgroup analysis will be performed that investigates the PROMIS scores (for pain intensity, fatigue, and bowel incontinence) at three months, and change in PROMIS scores for participants who receive the intervention, by disease type (Crohn's disease versus other IBD). Additionally, feasibility outcomes will be investigated by the four NHS Trusts/sites from which participants are recruited.

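### The three-month regressions are given a normal-approximation interval where the t interval is exact, and the small-sample fallback is a bootstrap of unnamed type

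*SAP*

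**What the plan says.** SAP section 6.8 restricts the three-month models to part of the sample: "For study participants who receive algorithm-informed interventions for treatable causes". Each outcome gets a linear regression "adjusting for the baseline measure of that outcome variable, IBD diagnosis (e.g., Crohn's disease or other IBD type), and NHS Trust". The next sentence lists the assumptions to be assessed, including normality and constant variance of the residuals.

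Two rules for the interval follow. The first is "If data are normally distributed, a normal approximation will be used to estimate 95%CIs". The second, for data that are not normal, is "bootstrap CIs will be estimated (using 1,000 bootstrap samples) because sample sizes may not be sufficiently large to invoke the central limit theorem". The only other fallback in the section is to drop Trust if a model does not converge.

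The section gives no expected number analysed, no t reference or degrees of freedom, no bootstrap type, and no rule for resamples that lose a covariate level. Section 6.10 repeats the PROMIS analyses by disease type. Section 6.5 states "A two-sided p-value and 5% alpha level will be used to declare" significance, then says that the focus is descriptive.

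**The concern.** The SAP itself raises the possibility of small samples, but its two rules do not clearly deal with it.

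- **Normal branch.** A normal quantile treats the residual variance as known. It is estimated, after fitting an intercept, a baseline slope, a diagnosis term and three Trust terms. Under normal errors the t quantile on the residual degrees of freedom gives exact coverage, so nothing is gained by the approximation.
- **Non-normal branch.** The bootstrap is chosen because the central limit theorem may not apply. The common forms (percentile, basic, normal-based) rest on large-sample arguments too, so the reason given does not support them. With Trust in the model, a simple resample may also contain nobody from a small Trust, and that Trust's coefficient then cannot be estimated.

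At stake is the stated confidence level of the intervals for change in symptoms and quality of life. By contrast, section 6.6 chooses the Wilson interval for proportions expressly to limit loss of coverage.

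**Working it through.** **What the SAP means by a normal approximation.** Its one precision figure uses the same phrase. Section 5.1a says "With a sample size of 200 participants, the width of the 95% confidence interval (CI") for a proportion "will be at most 13.9% (normal approximation CI"). The widest case is p = 0.5:

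2 × 1.96 × √(0.25/200) = 0.1386, or 13.9%.

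The figure is reproduced with the multiplier 1.96, so reading the phrase in section 6.8 as a 1.96-based interval is fair.

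**Inputs for the regression.** Trusts: four (section 6.10, "feasibility outcomes will be investigated by the four NHS Trusts/sites from which participants are recruited"). Diagnosis: two levels. Parameters: 1 intercept + 1 baseline + 1 diagnosis + 3 Trust = 6, so df = n − 6. The n values below are assumptions.

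**Normal branch, exact calculation.** Coverage of estimate ± 1.96 SE is 2·F(1.96) − 1, where F is the t distribution function on n − 6 df. The width ratio is t(0.975, df)/1.96.

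| n | df | t quantile | coverage of the z interval | t width / z width |
|---|---|---|---|---|
| 20 | 14 | 2.145 | 93.0% | 1.094 |
| 30 | 24 | 2.064 | 93.8% | 1.053 |
| 50 | 44 | 2.015 | 94.4% | 1.028 |
| 100 | 94 | 1.986 | 94.7% | 1.013 |

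If a subgroup model drops the diagnosis term, df = n − 5, and coverage at n = 20 is 93.1%.

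**Non-normal branch, simulation.** Six-parameter model, 95% interval for the adjusted mean, case resampling across Trusts, 1,000 resamples, 600 to 1,000 runs per cell. Assumed: a 40/30/20/10 Trust split, and normal or log-normal errors. Rank-deficient resamples were discarded. Simulation error is about ±1.5 to 2.5 points.

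| Errors | n | z | t | percentile bootstrap | studentised bootstrap |
|---|---|---|---|---|---|
| normal | 20 | 92.2% | 94.2% | 90.6% | 96.0% |
| normal | 30 | 93.3% | 94.7% | 92.1% | 94.8% |
| skewed | 20 | 89.1% | 90.9% | 88.2% | 93.4% |
| skewed | 30 | 90.1% | 91.9% | 90.2% | 94.4% |
| skewed | 50 | 91.9% | 92.2% | 91.4% | 93.3% |
| skewed | 100 | 90.2% | 90.5% | 90.8% | 93.0% |

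With skewed errors the percentile bootstrap does no better than the plain z interval. The t interval also under-covers, because skewness is the cause there and a wider quantile does not remove it. The studentised form comes closest to 95%.

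**Resamples that lose a Trust.** A Trust with k of n people is absent from a simple resample with probability (1 − k/n)^n. At n = 30: (29/30)^30 = 0.362, (28/30)^30 = 0.126 and (27/30)^30 = 0.042, so about 36%, 13% and 4% for k = 1, 2 and 3. With people allocated to Trusts at random in proportions 40/30/20/10, about 22% of resamples at n = 20 and 11% at n = 30 lacked a Trust.

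**The case against.** Several points on the other side stand.

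- **Loose wording.** Normal approximation may simply mean the usual regression interval, which standard software takes from t. If so, the normal branch has no error, only unclear text. Section 5.1a's use of the phrase for a 1.96-based interval makes the literal reading fair but does not prove it.
- **Data against residuals.** A reader might infer that the switch looks at the raw outcome instead of the residuals. The preceding sentence in section 6.8 already lists residual normality among the checks, so this is not a separate fault.
- **Bootstrap type.** A reader might infer that both branches must under-cover. The SAP names no bootstrap type, and the studentised bootstrap, which it permits, was close to nominal. What is wrong is that the choice is left open.
- **Dependence on error shape.** In another simulation of the six-parameter model, with a skewed 4-to-20 score with a floor at 4, bootstrap and t coverage were similar for n = 15 to 30 (93–94% against 92–95%). The bootstrap shortfall in the table above is therefore not a fixed quantity.
- **Sample size.** The study plans 200 participants and gives no n for these models. An n of 30 or fewer means at most 30/200 = 15% of the plan analysed in a model, and nothing in the SAP shows that this will happen. The disease-type subgroups are where it is most plausible.
- **Consequence.** Section 6.5 sets a 5% level but calls the focus descriptive. These are secondary outcomes in a study refocused on feasibility, and Tables 7 and 9 show adjusted means without a p-value column.

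**Conclusion.** The point holds as a minor one. Read literally, the normal branch gives intervals that are too narrow by a known amount: 2.0 percentage points of coverage at n = 20, 1.2 at n = 30, 0.6 at n = 50 and 0.3 at n = 100. These figures assume normal errors, six parameters and the stated n. In the non-normal branch the bootstrap is under-specified: the percentile form does not deliver what the SAP wants from it, and nothing says what happens when a resample loses a Trust.

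It would go too far to conclude that the three-month intervals will under-cover. That depends on how many people receive an intervention and return the questionnaire, on the shape of the residuals, and on which bootstrap is run, and the SAP fixes none of these. Nor does the evidence support using t throughout: with skewed errors t covered only about 91–92% at n = 20 to 30.

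**What to change.** Replace the two interval sentences in section 6.8 with wording to this effect: when residuals are approximately normal, 95% CIs are based on the t distribution with the model's residual degrees of freedom; when they are not, the reported 95% CI is a studentised bootstrap with 1,000 samples, resampled within NHS Trust. State that the same rule applies to the subgroup models in section 6.10.

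Resampling within Trust keeps every Trust in every resample. The simulation above resampled across Trusts, so the stratified studentised form was not itself tested.

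The cost is SAP wording only; no new data are needed. In the normal branch intervals widen by 9.4% at n = 20, 5.3% at n = 30, 2.8% at n = 50 and 1.3% at n = 100. In the skewed simulation the studentised interval was wider than the t interval by 41% at n = 20, 25% at n = 30, 14% at n = 50 and 7% at n = 100. So the widening is slight in the normal branch but noticeable if samples are both small and skewed.

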6.9 Interim analyses

Interim analyses of OPTIMISE study data will not be performed.

6.10 Subgroup analyses

A subgroup analysis will be performed that investigates the PROMIS scores (for pain intensity, fatigue, and bowel incontinence) at three months, and change in PROMIS scores for participants who receive the intervention, by disease type (Crohn's disease versus other IBD). Additionally, feasibility outcomes will be investigated by the four NHS Trusts/sites from which participants are recruited.

6.11 Sensitivity analyses

To assess the extent to which study results are affected by missing data, a sensitivity analysis will be performed on imputed data for primary clinical outcomes (23). The proportion of missing values for each variable will be assessed using numerical and graphical summaries. Univariable associations between missing values of each variable and observed values of other variables will be examined to understand how reliably a missing value might be imputed (18). This will be performed by constructing separate logistic regression models after creating a binary indicator variable for each variable with missing values coded as "1" and non-missing values coded as "0". The most applicable missing data mechanism will be informed by clinical knowledge of independent and dependent variables, reasons for missingness, and relationships between missingness and the observed values of collected variables.

Multivariate Imputation using Chained Equations (MICE) will be used to impute missing data under the expectation that both independent and dependent variables will have missing values and the data will not be monotonic missing (19). MICE replaces missing values with a random sample of plausible, imputed values drawn from their predictive distribution (20). First, an 'imputation' step will be performed, which involves constructing an imputation model that replaces missing data with one set of plausible values. Assuming that missing data are 'Missing At Random', the imputation model will specify a conditional distribution for missing values of each variable given the observed values of other variables. This imputation model will repeatedly replace missing values with a random sample of plausible values, creating a completed dataset with each imputation. The number of imputations (and thus completed datasets generated) will mirror the proportion of participants with at least one missing value. For example, 25 complete datasets will be generated if 25% of study participants have at least one missing value (21).

A logistic regression model will be used for missing values of binary variables and a multinomial logistic regression model will be selected for missing values of categorical variables with three or more unordered categories. Missing values of categorical variables with three or more ordered categories will be modelled using ordinal logistic regression and a linear regression model will be specified for continuous variables with missing data. Auxiliary variables – that is, variables that are not included in the intended analysis of imputed variables but are the highly correlated with the imputed variables (or its missingness) – will be included in the imputation model (21). Due to the descriptive nature of specified statistical analyses, no interaction terms or transformations will be included in the imputation model.

Next, an 'estimation' step will be conducted, whereby specified descriptive analyses – as described in sections 6.6 and 6.7 – will be performed separately for each completed dataset that is generated during the imputation step. Finally, a 'pooling' step will be performed, whereby point estimates (e.g., sample means) and measures of precision (e.g., standard deviations) estimated in each dataset will be aggregated using Rubin's Rules to create a final estimate that accounts for between- and within-imputation uncertainty (22).

PCTU_TEM_ST_02 Statistical Analysis Plan template v3.0 Study IBD-BOOST OPTIMISE Document version 1.0

7. Other analyses, data summaries, and graphs

Other data summaries

Safety analyses

The number and proportion of participants experiencing (i) adverse events (AEs) and (ii) serious adverse events (SAEs) will be tabulated, stratifying by whether or not algorithm-informed interventions were indicated. An AE is defined as any clinical change, disease, or disorder experienced by the participant during their participation in the study, whether or not considered related to the use of the intervention being studied. An AE is defined as serious (i.e., an SAE) if it results in one of the following outcomes:

- A life-threatening AE
- In-patient hospitalisation or prolonged hospitalisation not related to IBD flares, which are expected events
- Persistent or significant disability/incapacity
- A congenital anomaly/birth defect in the offspring of a subject
- Is otherwise considered medically significant by the investigator
- Other medical events requiring intervention to prevent one of the above outcomes.

Graphs

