	 Clinical outcomes The proportion of patients with any of the following, detected using the self-report symptom checklist, faecal calprotectin test, or by the nurse/clinician following the algorithm: "Red flags" on the self-report symptom checklist that require investigation (as a single binary indicator variable). Active disease (defined as faecal calprotectin ≥200 and/or IBD control score ≤13). Participants for whom interventions for fatigue are advised or prescribed (based on detected blood test abnormalities). Participants for whom interventions for pain are advised or prescribed (based on irritable bowel syndrome or functional dyspepsia, as diagnosed from responses on checklist). Participants for whom interventions for faecal urgency are advised or prescribed (based on the detection of untreated loose stool). 		

4. Outcome measures

As the IBD-BOOST Optimise study had to be adapted due to covid-19, with reduction of planned sample size from 500 to 200, the main focus of analysis will be on feasibility outcomes:

- Proportion of consenting participants who:
 (iii) completed the symptom checklist
 (iv) returned the postal faecal calprotectin test
- Proportion of participants for whom, after returning both the symptom checklist and faecal calprotectin test, no algorithm-informed action was indicated (and thus could progress to the RCT)
- Proportion of participants for whom algorithm-informed action was indicated where the clinical team completed and returned the CRF (to indicate the actions they planned)
- Of participants where algorithm-informed actions were indicated, the proportion who completed outcome measures at three months (i.e., attrition rates).
- Number and proportion of participants consenting to receive the algorithm-informed intervention but then discontinuing (with reasons if possible). Discontinuing will be defined as actively notifying study personnel of withdrawal or failing to respond to the OPTIMISE questionnaire at three months if it was indicated.

4.1 Primary clinical outcome measures (upon administration of the self-report symptom checklist and faecal calprotectin test, before delivery of algorithm-informed intervention(s)):

The proportion of patients with any of the following, detected using the self-report checklist, faecal calprotectin test, or by the nurse/clinician after implementing the algorithm:

- "Red flags" on the self-report symptom checklist that require investigation (as a single binary indicator variable).

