- Active disease (defined as faecal calprotectin \geq 200 and/or IBD control score \leq 13).
- Participants for whom interventions for fatigue are advised or prescribed (based on detected blood test abnormalities).
- Participants for whom interventions for pain are advised or prescribed (based on irritable bowel syndrome or functional dyspepsia, as diagnosed from responses on checklist).
- Participants for whom interventions for faecal urgency are advised or prescribed (based on the detection of untreated loose stool).

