6.6 Analysis of the primary clinical outcomes

To fulfil the primary study objective, the proportion of study participants with (i) red flags, (ii) active IBD disease, (iii) blood test abnormalities (in participants with fatigue), (iv) irritable bowel syndrome or functional dyspepsia (in participants with pain), and (v) untreated loose stool (in participants with urgency) will be estimated. We will construct 95%CIs around proportion estimates using Wilson's Score Interval to minimize the loss of coverage that typically occurs with normal approximations of the Wald Interval. Complete case analyses (ignoring missing data) will be performed for primary outcomes.

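### Section 6.11 bars transformations in the imputation model and does not say how active disease is imputed; if skewed calprotectin is imputed on the raw scale and cut at 200, the imputed proportion is biased

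*SAP*

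**What the plan says.** The primary clinical outcomes are analysed on complete cases (SAP section 6.6): "Complete case analyses (ignoring missing data) will be performed for primary outcomes". Section 6.11 adds that "a sensitivity analysis will be performed on imputed data for primary clinical outcomes", and Table 10 sets the two sets of results side by side.

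Section 6.11 chooses the imputation model by variable type. For continuous variables, "a linear regression model will be specified for continuous variables with missing data". For binary variables, "A logistic regression model will be used for missing values of binary variables". It then says that "no interaction terms or transformations will be included in the imputation model", and gives the descriptive nature of the analyses as the reason.

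One outcome in Table 10 is a composite with a laboratory cut-off (section 3 summary table and section 4.1): "Active disease (defined as faecal calprotectin ≥200 and/or IBD control score ≤13". Return of the postal calprotectin test is itself a feasibility outcome (section 4), so the plan expects that some results may be missing.

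The SAP does not say whether active disease is imputed directly as a binary variable or derived from imputed calprotectin and IBD-Control. It gives no calprotectin distribution and no expected missing rate.

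**The concern.** The reason given for barring transformations can serve for a mean. It does not serve for a proportion above a threshold, which depends on the shape of the imputed distribution. A linear regression imputation draws from a normal distribution around the fitted value. If the real variable is positive and right-skewed, its standard deviation is inflated by the upper tail. The normal draws then spread symmetrically: some fall below zero, and the share above 200 is wrong even when the data are missing completely at random.

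Table 10 is the SAP's only specified check of how far missing data affect the primary clinical outcomes. A shift in the active-disease row that comes from the imputation model could be taken for an effect of missingness.

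**Working it through.** **The plan's own precision figure.** Section 5.1a gives a maximum 95% CI width of 13.9% for 200 participants. 2 × 1.96 × √(0.25/200) = 0.1386, so it is reproduced; the half-width is about 7 points. The SAP has no figure for calprotectin to reproduce.

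**Assumptions, none of them in the SAP.** Calprotectin is log-normal with median *m* and log-SD *s*; 30% is missing completely at random; half of participants score 13 or less on IBD-Control; the correlation between log calprotectin and a worse score is 0.3. Each is varied below except the correlation.

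**Step 1: calprotectin ≥200 alone, closed form with weak predictors.**
- True share: 1 − Φ((ln 200 − ln *m*)/*s*).
- Raw-scale normal draws: 1 − Φ((200 − μ)/σ), with μ = *m*·exp(*s*²/2) and σ = μ·√(exp(*s*²) − 1).
- Overall bias: missing fraction × difference.

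Example, *m* = 100 and *s* = 1.3:
- μ = 233 and σ = 489.
- True share: 1 − Φ(0.533) = 29.7%.
- Raw-scale share: 1 − Φ(−0.067) = 52.7%.
- Imputed values below zero: Φ(−233/489) = 32%.
- Bias at 30% missing: 0.30 × (52.7 − 29.7) = +6.9 points.

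Over medians 50, 100 and 150 and log-SD from 0.8 to 1.5, 10 of 12 scenarios give +3.7 to +8.4 points; the other two give −0.6 and +1.7. Between 14% and 37% of imputed values are negative.

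**Step 2: the composite.** A missing calprotectin matters only for a participant scoring above 13. With half above 13, independence scaling of the example gives 6.9 × 0.5 ≈ 3.5 points. Simulation of the composite (n = 200, 400 replicates, calprotectin imputed given the IBD-Control score) gives:

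| Median, log-SD, missing | True | Raw-scale imputation | Log-scale imputation |
|---|---|---|---|
| 100, 1.3, 30% | 60.5% | 64.2% | 60.7% |
| 100, 1.3, 15% | 60.5% | 62.3% | 60.5% |
| 100, 1.0, 30% | 58.2% | 61.0% | 58.3% |
| 50, 1.3, 30% | 54.7% | 57.4% | 54.6% |

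**Step 3: wider range.** Bias in the composite at 30% missing, over log-SD 0.8 to 1.75 (60 replicates per scenario, so differences under about half a point are noise):

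| Assumed median | Bias, percentage points |
|---|---|
| 30 | −0.1 to +3.8 |
| 50 | 0.0 to +4.5 |
| 80 | +0.6 to +4.5 |
| 100 | +1.6 to +4.0 |
| 150 | +2.2 to +3.3 |
| 200 | +2.2 to +2.5 |
| 300 | +0.5 to +1.0 |
| 400 | −0.5 to +0.3 |
| 500 | −1.7 to −0.3 |

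For calprotectin ≥200 alone, the share among imputed values is within about 2 points of the truth at a median of 300 and is understated by 5 to 12 points at medians of 400 to 500. The composite turns negative later, because the participants who matter score above 13 and tend to have lower calprotectin.

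At median 80 and log-SD 1.25 the composite bias is +4.6, +3.3 and +2.1 points when 30%, 50% and 70% score 13 or less.

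**Step 4: alternatives.** In the same scenarios, log-scale imputation stays within about 0.5 point. So does logistic imputation of calprotectin ≥200, except in one scenario with almost no values above the cut (+2.9).

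**The case against.** The strongest objection is that the SAP never says calprotectin is imputed as a continuous value. The sensitivity analysis is aimed at the primary clinical outcomes, all of them binary, and section 6.11 gives logistic regression for binary variables. On that reading the bias essentially disappears. This stands, and it makes the point conditional. But section 6.11 assigns models to variables by type and then analyses each completed dataset, so linear imputation of a continuous laboratory value is an equally natural reading. The two readings can give different answers, and the SAP does not choose between them.

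The direction and size rest on inputs the SAP does not give. This also stands: the bias shrinks with less missingness and reverses when most values lie well above 200.

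The shift is within the 13.9% interval width. That is true, but the width describes sampling error in one estimate, whereas Table 10 compares two estimates from the same participants.

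A reader might also infer that Table 10 would falsely signal missing-data bias whenever data are missing completely at random. The SAP does not support that, because it does not say how the complete-case analysis counts participants who score 13 or less but lack calprotectin. They already meet the and/or definition. If they are kept, the complete-case figure in the first example is itself too high: (50 + 0.7 × 10.5)/(50 + 0.7 × 50) = 57.35/85 = 67.5%, against a truth of 60.5%. The raw-scale imputed figure of 64.2% would then be the closer one. Only if they are excluded is the complete-case column unbiased and the shift an artefact of the model.

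**Conclusion.** The point holds conditionally. The ban on transformations is justified by a reason that fails for an outcome defined by a threshold, and the level at which active disease is imputed is left open. If calprotectin is imputed as a continuous value and is right-skewed, raw-scale imputation is typically about 2 to 4 points too high for active disease, given a median of about 50 to 150, 30% missing and half of participants scoring 13 or less. It is near zero at medians of 300 to 400 and negative at 500.

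Two stronger readings are not supported. The SAP does not establish that its sensitivity analysis will overstate active disease, since logistic imputation of a binary variable is also within its text. The 3.7 to 8.4 points apply to calprotectin ≥200 alone, not to active disease. Nor does anything here show that IBD-Control needs a different imputation model.

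The consequence is limited to one row of a sensitivity table in a descriptive study whose main focus is feasibility. The complete-case primary analysis is not affected.

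**What to change.** In section 6.11, lift the ban on transformations for faecal calprotectin and state one method for active disease:

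- impute calprotectin on the log scale (or by predictive mean matching), back-transform, and derive active disease from calprotectin and IBD-Control after imputation; or
- impute the indicator calprotectin ≥200 by logistic regression and combine it with IBD-Control. This is equally simple, but can be unstable if very few values reach 200.

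The cost is one sentence in the SAP and one option in the imputation code. No new data are needed.

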6.7 Checklist and algorithm feasibility

The analysis of feasibility outcomes will be performed in the same way as the analysis of the clinical outcomes – that is, as descriptive statistics with corresponding 95% CIs. All feasibility outcomes are presented in Table 8.

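### Section 6.11 names the wrong precision measure for Rubin's Rules, re-runs feasibility outcomes on imputed data against its own scope, and leaves the interval for an imputed proportion undefined

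*SAP*

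**What the plan says.** Section 6.6 estimates five primary clinical proportions from complete cases. It chooses Wilson's "Score Interval to minimize the loss of coverage" that it attributes to Wald intervals.

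Section 6.7 reads: "The analysis of feasibility outcomes will be performed in the same way as the analysis of the clinical outcomes". The outcomes it covers, listed in Section 4, are mainly completion, return and discontinuation rates.

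Section 6.11 opens by limiting the imputation exercise: "a sensitivity analysis will be performed on imputed data for primary clinical outcomes". Table 10 matches this. It lists the five primary clinical outcomes and gives n (%) for complete-case and imputed data. Later in 6.11 the estimation step repeats the descriptive analyses "as described in sections 6.6 and 6.7" in each completed dataset. The pooling step then states that "measures of precision (e.g., standard deviations) estimated in each dataset will be aggregated using" Rubin's Rules, with the aim of reflecting uncertainty both within and between imputations.

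**The concern.** Three parts of the imputation plan do not work as written.

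- **Quantity pooled.** A standard deviation describes the spread of individual values. A standard error describes the uncertainty of an estimate. Rubin's Rules need the latter, squared. Putting in the former inflates the within-imputation variance by a factor of n.
- **Scope.** For a completion or return rate, non-return is the result itself and not a gap to be filled. Naming 6.7 in the estimation step therefore makes little sense, and it contradicts both the opening sentence of 6.11 and Table 10.
- **Interval type.** Section 6.6 rejects the Wald interval. Rubin pooling of a raw proportion and its variance leads back to a symmetric Wald-type interval, and nothing says how the Wilson form is to be kept.

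At stake is whether the imputed results can be set beside the complete-case results on equal terms. The primary complete-case results are not at stake.

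**Working it through.** **Inputs from the SAP.** n = 200 and a 95% interval whose width "will be at most 13.9% (normal approximation CI") (Section 5.1a); two-sided 5% level (Section 6.5), so z = 1.96; Wilson intervals (Section 6.6).

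**Assumptions not in the SAP.** Proportion p = 50% or 5%; fraction of missing information f = 10% or 25%; normal quantile for the pooled interval.

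1. *The plan's own figure.* Width = 2 × 1.96 × √(0.25/200) = 0.1386, or 13.9%. It reproduces, with a half-width of 0.069. It does not bear on imputation, for which the SAP states no figure.

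2. *Rubin's total variance, correctly formed.* T = W + (1 + 1/m)B, with W = p(1−p)/n. For missing information f, (1 + 1/m)B = W × f/(1−f), so T = W/(1−f). At p = 50%, W = 0.25/200 = 0.00125.
   - f = 10%: T = 0.00125/0.90 = 0.001389; half-width 1.96 × √T = 0.073.
   - f = 25%: T = 0.00125/0.75 = 0.001667; half-width 0.080.

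3. *The same, with the standard deviation put in literally.* W becomes p(1−p) = 0.25 and the between-imputation term is unchanged.
   - f = 10%: total 0.25 + 0.000139; half-width 0.980.
   - f = 25%: total 0.25 + 0.000417; half-width 0.981.

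   An interval of ±0.98 around 0.5 exceeds the whole 0 to 1 range.

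4. *Ratio of literal to correct width.* Dividing the totals gives √(n(1−f) + f), which does not depend on p. At n = 200 this is √180.1 = 13.4 for f = 10%, √150.25 = 12.3 for f = 25%, and √200 = 14.1 with nothing missing. With a smaller denominator the factor falls: at n = 100 with nothing missing it is √100 = 10.

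5. *Wilson against Wald after pooling.* At p = 5% and f = 25%, T = (0.0475/200)/0.75 = 0.000317. The symmetric interval is 5% ± 1.96 × √0.000317 = 5% ± 3.5 points, or 1.5% to 8.5%. A Wilson interval on the same variance uses effective n = 0.0475/0.000317 = 150 and gives 2.5% to 9.7%. Both limits move by about 1 point. At p = 50% and f = 25% the two forms are 42.0% to 58.0% and 42.1% to 57.9%, practically the same.

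6. *Scope, set side by side.* The opening sentence of 6.11 covers primary clinical outcomes only. Table 10 has five primary clinical rows and no feasibility row. The estimation step covers 6.6 and 6.7. The third statement cannot stand with the first two.

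**The case against.** The strongest reply is that *standard deviations* is only an example in brackets. The same sentence names the right method and the right aim, and an analyst using standard multiple-imputation software would pool standard errors anyway. The companion example, sample means, does not fit proportions either, which suggests generic wording. This stands as far as it goes: a reader might infer that the reported imputed intervals will be wrong, and the document does not show that. What it shows is a written instruction that gives a useless interval if obeyed.

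It can also be said that Table 10 has no interval column, so no imputed interval is promised. That is weak. Section 6.5 makes 95% intervals the default, and Table 4 also shows only n (%) although Section 6.6 requires intervals for those same outcomes.

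Three further readings are tempting and are not supported:

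- *Imputation runs on feasibility instead of the three-month scores.* Section 6.6 is covered, and the scores of Section 6.8 are left out by the explicit scope sentence and by Table 10. Whether 6.7 was meant to be 6.8 cannot be settled from the SAP.
- *An imputed return rate would read 100%.* Whether an item came back is observed for everyone, and chained equations fill only missing values. The figure needs return status to be re-derived from filled-in data, which the SAP does not describe.
- *This is the only look at missing data.* Section 6.2 reports missingness for every variable, Tables 6 and 7 tabulate missing scores, and three-month attrition is itself a feasibility outcome.

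Finally, a proportion has a standard error whichever interval is reported, so Wilson intervals do not prevent pooling. They only leave the form of the pooled interval open.

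**Conclusion.** The point holds as two misstated rules and one undefined interval, all within a sensitivity analysis.

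The precision measure is wrong as written. Taken literally at n = 200, it widens the interval for a proportion 12.3- to 13.4-fold for 25% to 10% missing information, and 14.1-fold with none. These factors rest on the assumed missing information and on all 200 participants contributing; outcomes assessed in fewer participants would give smaller factors.

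The reference to 6.7 contradicts the section's own scope and Table 10, whatever rates are observed. The Wilson gap is minor, about 1 point at p = 5% under 25% missing information and negligible near 50%.

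Section 6.8 states no missing-data method for the three-month scores, and a reader might count that as a further error. It is better seen as a choice open to debate: these are secondary outcomes in a study whose analysis Section 6.5 calls descriptive, and the planned regression already adjusts for the baseline score, diagnosis and Trust.

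**What to change.** In Section 6.11:

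1. Replace *standard deviations* with *standard errors (squared, as the within-imputation variance)*, and replace the example of sample means with proportions.
2. Delete the reference to Section 6.7 and state that feasibility outcomes are not imputed.
3. State that proportions are pooled on the logit scale and back-transformed, or that a multiple-imputation Wilson interval is used.

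In Table 10, add a 95% CI column for both the complete-case and the imputed results.

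The cost is a few lines of SAP text and modest programming, with no change to data collection or to the primary analysis. As an optional extension, the sponsor could add a missing-data sensitivity analysis for the three-month scores of Section 6.8, or say why none is planned.
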